8.4.4. Reporting of Pregnancy

While pregnancy itself is not considered an AE, pregnancy occurring in a clinical study must be followed to collect information regarding the experiences of gestation and pregnancy with study agent exposure. The investigator must report any pregnancy that occurs in a female study participant or female partner of a male participant subsequent to first exposure to the study agent until the EOT visit, or 3 months following a participant's last dose in the event of early withdrawal. All pregnancies will be reported to the IRB/IEC, Sponsor, and CRO. In the event of a pregnancy, treatment will be discontinued, and the participant will undergo continued safety follow up through pregnancy outcome. The study blind can be broken for safety reasons if the information is required for the management of pregnancy. Any noted intentional or unintentional breaking of the blind should be reported to the Sponsor's study team lead and quality group (see [Section 10.6.3](#)).

Any pregnancy must be followed by the investigator until delivery or to the end of pregnancy. Any anomalies, complications, abnormal outcomes, or birth defect(s) observed in the child must be reported as an SAE within 24 hours of the investigator or study personnel's first knowledge.

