6.1.4. Dosing and Administration

Study drug will be self-administered orally b.i.d., approximately 12 hours apart. AKST4290 will be administered as a TDD of 800 mg (400 mg b.i.d.). Matching placebo will be self-administered orally b.i.d. following the same dosing instructions as AKST4290.

Participants will receive training on study drug administration prior to initial study drug administration at Visit 2. Study drug will be self-administered in the clinic under the supervision of study personnel during every in-clinic visit of the Treatment Period (Visits 2-8) after any pre-dose assessments (including PK sample collection), and then self-administered at home between study visits.

When study drug is dispensed, participants will receive a total of 5 packets, which represents a 5-week supply (4 weeks of treatment plus an additional week). Study drug accountability will be assessed by packet.

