7.3.2. Treatment

The 24-week Treatment Period comprises Visit 2 (Baseline/Day 1) through Visit 8 (EOT/ET/Day 168). The assessments to be performed at each visit during the Treatment Period are detailed in the Schedule of Events in [Section 15](#).

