8.1.2. Definition of Serious Adverse Events

Note: if either the investigator or the Sponsor believes that the event is serious, the event must be considered serious and evaluated for expedited reporting.

Note: the terms “severe” and “serious” are not synonymous. Severity (or intensity) refers to the grade of an AE. “Serious” is a regulatory definition.

A SAE (experience) or reaction is an untoward medical occurrence that, at any dose, fulfills one or more of the following criteria:

- a. Results in death (i.e., the AE actually causes or leads to death).
- b. Is life-threatening.
 - An AE is considered “life-threatening” if, in the view of either the investigator or Sponsor, its occurrence places the patient or participant at immediate risk of death; it does not include AEs which, had it occurred in a more severe form, might have caused death.
- c. Results in inpatient hospitalization or prolongation of existing hospitalization.
 - Hospitalization for elective treatment of a pre-existing condition that did not worsen during the study is not considered an AE; hospitalization for participating in this study is not considered an AE.
 - Complications that occur during hospitalization are AEs; if a complication prolongs hospitalization, the event is an SAE.
 - “Inpatient” hospitalization means the participant has been formally admitted to a hospital for medical reasons that may or may not be overnight; it does not include presentation at a casualty or emergency room unless the event meets the definition of an Important Medical Event (in the opinion of the Investigator or Sponsor).

- d. Results in persistent or significant incapacity or substantial disruption of the ability to conduct normal life functions.
 - The term 'disability' means a substantial disruption of a person's ability to conduct normal life functions; this definition is not intended to include experiences of relatively minor medical significance such as uncomplicated headache, nausea, vomiting, diarrhea, influenza, accidental trauma (i.e., sprained ankle) that may interfere or prevent everyday life functions but do not constitute a substantial disruption.
- e. Results in a congenital anomaly in the offspring of a participant who received drug.

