8.3.1. Post-Study Adverse Event and Serious Adverse Event

The investigator is not obligated to actively seek SAE information in former study participants, but the investigator is encouraged to notify Alkahest, Inc. or their designee of any AE or SAE occurring within 30 days after a participant completes the study (or has their last visit) that the investigator judges may be reasonably related to study treatment or study participation.

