15. SCHEDULE OF EVENTS

Table 2 **Schedule of Assessments**

Visit Number Week Day Time Window (days) ^a	Screening		Treatment							Follow-up
	1	2 (Baseline) 1 -28 to -2	3 4 28 ±3	4 8 56 ±3	5 12 84 ±3	6 16 112 ±3	7 20 140 ±3	8 (EOT/ET) ^b 24 168 ±3	9 (EOS) 28 196 ±3	
Informed consent and optional consent for aqueous humor sample collection ^c	X									
Informed consent for DNA banking ^d	X									
Demographics	X									
Medical history	X									
Inclusion/exclusion criteria ^e	X	X								
Physical examination	X	X							X	
Vital signs (seated)	X	X	X	X	X	X	X	X		
Pregnancy test (in WOCBP) ^f	X	X	X	X	X	X	X	X		
Laboratory tests ^g	X	X	X	X	X	X	X	X		X
12-lead electrocardiogram	X								X	X
HbA1c			X		X				X	
Extended ophthalmoscopy	X	X	X	X	X	X	X	X		X
Slit lamp examination	X	X	X	X	X	X	X	X		X
Intraocular pressure	X	X	X	X	X	X	X	X		X
Gonioscopy	X	X		X		X		X		X
SD-OCT	X	X	X	X	X	X	X	X		X
OCT-A (if available at the site) ^h			X						X	
Visual acuity ⁱ	X	X	X	X	X	X	X	X		X
Fundus photography	X	X	X	X	X	X	X	X		X
Fluorescein angiography ^j	X				X			X		
VF with perimetry and/or microperimetry (if available at the site) ^h			X						X	
Workplace Productivity and Activity Impairment General Health questionnaire			X		X		X		X	
Administration of study agent ^k			X	X	X	X	X	X		
Dispense study agent			X	X	X	X	X	X		
Study agent accountability			X	X	X	X	X	X	X	

Visit Number Week Day Time Window (days) ^a	Screening		Treatment							Follow-up
	1	2 (Baseline)	3	4	5	6	7	8 (EOT/ET) ^b	9 (EOS)	
	-28 to -2	1	4	8	12	16	20	24	28	
		1	28	56	84	112	140	168	196	
Optional aqueous humor collection ¹		X						X		
PK blood sample collection (for plasma extraction) ^m		X	X	X	X	X	X	X	X	
Biomarker plasma aliquots ^m		X						X	X	
Pharmacogenomics blood sample (and optional DNA banking sample)		X ^d								
Flow cytometry/CBC blood sample collection ^m		X						X		
Prior and concomitant medication review ⁿ	X	X	X	X	X	X	X	X	X	
Adverse events	X	X	X	X	X	X	X	X	X	
Study completion										X

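### Section 8.4.4 ends mandatory pregnancy reporting at the EOT visit for completers but 3 months after the last dose for early withdrawals, without explanation, and leaves pregnancies after EOT in completers not clearly reportable

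*Protocol*

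**What the plan says.** The reporting duty is in Protocol Section 8.4.4: "The investigator must report any pregnancy that occurs in a female study participant or female partner of a male participant subsequent to first exposure" to study agent. It runs "until the EOT visit, or 3 months following a participant's last dose in the event of early withdrawal". The same section says that pregnancies go to the IRB/IEC, sponsor and CRO, that they are followed to their end, and that an abnormality in the child is reported as an SAE within 24 hours of becoming known.

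Other places bear on the point:

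- Section 7.3.2 puts EOT at Visit 8, Day 168.
- Section 6.1.4 describes supervised dosing "during every in-clinic visit of the Treatment Period (Visits 2-8) after any pre-dose assessments", with home dosing between visits.
- Section 7.3.4 ends participation at Visit 9. Table 2 places that visit at Day 196.
- Section 8.1.1 excludes pregnancy itself from the definition of an AE. Section 8.1.2(e) lists as a seriousness criterion: "Results in a congenital anomaly in the offspring of a participant who received drug".
- Section 8.3.1 covers the time after the study only by saying that "the investigator is encouraged to notify Alkahest, Inc. or their designee of any AE or SAE occurring within 30 days" of completion or last visit, and only for events judged reasonably related.
- Section 5.2, criterion 23, asks a woman who is or may be pregnant to tell her treating physician while she or her partner is in the study.

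**The concern.** The stated purpose of Section 8.4.4 is to learn what happens in pregnancies with study agent exposure. By following early withdrawals for 3 months after the last dose, the sponsor treats the post-dose interval as relevant. A completer has had the full 24 weeks of drug, yet the required window closes at about the last dose. Nothing in either document says why completing treatment should make the interval after it irrelevant.

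What is at stake is reproductive-safety information. If a site does not have to report a pregnancy, follow-up to outcome may never start, and an anomaly can be reported as an SAE only if someone at the site hears of it. No endpoint, estimand, sample size or analysis depends on this.

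**Working it through.** There is no figure in the plan to reproduce. The check sets the passages side by side and counts days.

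**Inputs**

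| Item | Value | Source |
|---|---|---|
| EOT visit | Visit 8, Day 168 (±3) | Protocol 7.3.2, Table 2 |
| Last dose in completers | on or about Visit 8 | Protocol 6.1.4, Table 3 |
| End of participation | Visit 9, Day 196 | Protocol 7.3.4, Table 2 |
| End of window, completers | EOT visit | Protocol 8.4.4 |
| End of window, early withdrawals | last dose + 3 months | Protocol 8.4.4 |
| Planned enrolment and completers | about 80 and 69 | Protocol 5.6.2 |

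The administration row of Table 2, as extracted, has six marks, while Section 6.1.4 names seven visits. Table 3 times the Visit 8 PK sample before a dose. Even if Visit 8 were undosed, twice-daily home dosing runs up to it, so the last dose falls at or just before EOT either way.

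**Required reporting time after the last dose**

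- Completers: Day 168 − Day 168 = about 0 days.
- Early withdrawals: 3 × 365.25 / 12 = 91.3 days. This takes an average month as an assumption; real calendar months shift it by a day or two.

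**Contact after EOT in completers**

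- EOT to Visit 9: 196 − 168 = 28 days. If EOT moves within its window, 196 − 171 = 25 to 196 − 165 = 31 days.
- Part of a 3-month period lying beyond Visit 9: 91.3 − 28 = about 63 days, with no scheduled contact.

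**Share under each window, by plan**

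- Completers: 69/80 = 86.25%.
- Others: 11/80 = 13.75%.

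These are shares of all participants, not of those at risk of a pregnancy.

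**Testing at Visit 9.** The pregnancy-test row of Table 2 has eight marks, like the vital-signs row, and SAP Section 3.4.2.3 says that vital signs run from Screening to Visit 8. The laboratory row has nine marks. The natural reading is that no pregnancy test is marked at Visit 9 although laboratory samples are taken then. The table layout was damaged in extraction, so this placement is inferred.

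**Reading the window.** The sentence in 8.4.4 can be taken in two ways. If the EOT limit attaches to when the pregnancy occurs, one conceived on drug and recognised at Visit 9 is reportable, and only conceptions after EOT fall outside. If the limit attaches to the duty to report, late-recognised pregnancies fall outside too. The text does not say which. On either reading, a completer's pregnancy that begins after EOT has no clear mandatory report, while the same pregnancy in an early withdrawal has one for about 91 days.

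**The case against.** A reader might infer that drug-exposed pregnancies in most participants are never captured and that their outcomes go untracked. The documents do not support that, for these reasons:

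- The sentence in 8.4.4 is worded around when a pregnancy occurs. One conceived before EOT can fairly be read as inside the window whenever it is found, and it would then be followed to its end.
- Section 5.2, criterion 23, keeps the woman's request to notify alive until participation ends at Visit 9, which is an attended visit.
- The sentence in 8.4.4 on sending pregnancies to the IRB/IEC, sponsor and CRO carries no time limit of its own.
- Anomalies are reportable as SAEs on first knowledge, with no EOT cut-off.
- The 86% is the planned completer share. Only women of childbearing potential and men with female partners matter. Neither is counted, and such women must agree to highly effective contraception.
- A conception after the last dose is drug-exposed only if drug or its effect persists. The readable text gives no elimination time or reproductive toxicity data, and background sections are redacted.

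All of this stands against the strong reading. It does not close the gap. Criterion 23 tells a woman to inform her physician but creates no investigator report, and it lapses at Visit 9. The sentence on recipients directly follows the windowed one, so a site can reasonably take it as bounded by that window. SAE reporting on first knowledge depends on the site still being in touch. Section 8.3.1 does not help, because pregnancy is not an AE and the notification is encouraged rather than required.

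**Conclusion.** The inconsistency is real, but it is narrower than a total failure of capture. Section 8.4.4 gives completers about 0 days of required reporting after the last dose and early withdrawals about 91, with no reason given. As written, investigators are not clearly required to report pregnancies after EOT in completers or their female partners, no pregnancy test appears to be marked at Visit 9, and the status of a pregnancy conceived on drug but recognised after EOT is left open.

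Three limits apply. The number at risk among the planned 69 completers is unknown. Whether conceptions after EOT are exposed cannot be judged from the readable text. The effect in this study is probably nil: SAP Sections 1 and 4.6 report 3 participants on drug when it was terminated, all told to stop. Protocol Section 5.6.1 lists a sponsor request among the reasons for withdrawal, so they probably fall under the 3-month window. That last step is an assumption. The point therefore concerns the protocol text and any later protocol that reuses it.

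**What to change.** Reconcile Section 8.4.4 so that a single reporting window, counted from the last dose, applies to completers and early withdrawals alike. The sponsor should confirm its length; no figure is proposed here. State that a pregnancy conceived within the window is reportable whenever it is recognised. Align the notification text in Section 5.2, criterion 23, and the Visit 9 column of Table 2 with that window. For the terminated study, the sponsor should record which window was applied to the 3 participants.

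The cost is a sentence or two in 8.4.4 with matching edits elsewhere, a pregnancy question at the existing Visit 9, possibly one later contact for those concerned, and a few more reports to process.

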8.5. Study Halting Rules

The Data Safety Monitoring Board (DSMB) will make recommendations concerning the continuation, modification, or termination of the study.

8.6. Safety Oversight

Safety oversight will be provided by the Sponsor's program physician or his or her designee and the CRO's medical monitor(s) in concert with the site investigators. Additionally, a DSMB will be established. Members of the DSMB will be independent from the study conduct and free of actual or perceived conflict of interest.

The DSMB will meet at least quarterly (or more frequently as needed) to assess safety data. The DSMB will operate under the rules of an approved charter that will be written and reviewed at the organizational meeting of the DSMB. At this time, each data element that the DSMB needs to assess will be clearly defined. The DSMB will provide its input to Alkahest, Inc.

In addition, the Sponsor will perform ongoing monitoring of cumulative safety data in a systematic manner to ensure that any safety signals that may impact the overall benefit/risk ratio in this specific population will be detected, assessed, and any necessary action taken. Blinded cumulative safety data (e.g., AE listings, vital sign plots, safety laboratory values, ECGs, physical examination results) will be reviewed by the CRO's Medical Monitor(s) and/or by the Sponsor's Program Physician throughout the study. If either physician detects any safety trends of concern, an ad-hoc meeting of the DSMB may be triggered.

9. CLINICAL MONITORING

Clinical site monitoring is conducted to ensure that the rights and wellbeing of human research participants are protected, that the reported study data are accurate, complete, and verifiable, and that the conduct of the study is in compliance with the currently approved protocol/amendment(s), with GCP, and with applicable regulatory requirement(s).

- Monitoring for this study will be performed by the study CRO in accordance with the Clinical Monitoring Plan (CMP).
- A mix of onsite and centralized risk-based monitoring will be performed to ensure the safety of clinical research participants and the accuracy and completeness of study data.
- The Sponsor will be provided with copies of monitoring reports per the timelines specified within the CMP.
- Details of clinical site monitoring tasks and scope are documented in the study's CMP. The CMP describes in detail who will conduct monitoring, at what frequency monitoring will be done, at what level of detail monitoring will be performed, and the distribution of monitoring reports.
- Independent audits may be conducted by the Sponsor's Quality Assurance (QA) function or Sponsor contracted QA consultants in accordance with a study specific QA plan to ensure monitoring practices are performed consistently across all participating sites, that monitors are following the CMP and sites conduct the study according to the protocol, GCP, and applicable regulatory requirements.

10. STATISTICAL CONSIDERATIONS

10.1. Statistical Design Model and Analytical Plans

A Statistical Analysis Plan (SAP) with analytical details and assumptions will be developed and finalized before database lock and unmasking of the study data.

10.2. Statistical Hypotheses

The primary efficacy endpoint is the proportion of participants with a ≥ 3 -step improvement in the DRSS score from baseline at Week 24. The null hypothesis to be tested is that there is no difference between AKST4290 (A) and placebo (P) in the proportion of participants with a ≥ 3 -step improvement at Week 24:

$$H_0: p_A = p_P$$

The alternate hypothesis is that there is a difference in the treatment group proportions:

$$H_1: p_A \neq p_P.$$

10.3. Analysis Datasets

The Intent-to-Treat (ITT) Population will include all participants allocated to a randomized treatment.

The Safety Population will include all participants who receive at least 1 dose of the study drug.

10.4. Description of Statistical Methods

10.4.1. General Approach

The ITT Population will be the primary population used for efficacy analyses. For the purposes of the efficacy analysis, the treatment assignment will be according to the randomization schedule.

The Safety Population will be the primary population used for the safety analyses. For the purposes of the safety analysis, the treatment assignment will be according to the treatment the participant actually received.

10.4.2. Analysis of the Primary Endpoint

The primary estimand is the difference between treatment groups in the proportion of participants with a ≥ 3 -step improvement from Baseline on the DRSS score at Week 24, among participants in the ITT Population. Participants who have missing data at the Week 24 time point will be considered non-responders. The proportion of participants with improvement at Week 24 will be compared among treatment groups using a Cochran-Mantel-Haenszel chi-square test, stratified by the DRSS category at Baseline (moderately severe or severe).

10.4.3. Analysis of the Secondary Endpoints

Analysis of the secondary endpoints will be based on the ITT Population.

The proportion of participants with a \geq 2-step improvement from Baseline on the DRSS score at Week 24, as well as the proportion of participants progressing to CI-DME, PDR, and/or requiring ASNV requiring treatment, will be analyzed using a similar method as described for the primary endpoint.

Time to the event of CI-DME, PDR, and/or ASNV requiring treatment will be summarized using Kaplan-Meier (KM) methodology. Participants who do not experience the event will be censored at the time of their last non-missing evaluation. AKST4290 will be compared to placebo using the stratified log-rank test, stratified by the DRSS category at Baseline (moderately severe or severe). Kaplan-Meier estimates of the survival distribution function over time will be plotted by treatment group.

Clinical changes in diabetic kidney disease related laboratory values (e.g., eGFR and UACR) will be analyzed by a mixed-effects model for repeated measures (MMRM). The model will include fixed effects for treatment group, categorical visit, treatment group by visit interaction, the DRSS category at Baseline (moderately severe or severe), and the relevant Baseline value as a covariate. An appropriate covariance structure will be selected prior to database lock and the Kenward-Roger approximation will be used to calculate the denominator degrees of freedom for the test of fixed effects.

Safety will be assessed through summaries of AEs, changes in laboratory test results, and changes in vital sign measurements. In addition, all SAEs, including deaths, will be listed and summarized separately.

10.4.4. Analysis of the Exploratory Endpoints

Changes in BCVA (gain or loss) using the ETDRS, macular volume, and CMT as assessed by SD-OCT, WPAI-GH questionnaire, and OCT-A over time will be analyzed using an MMRM model similar the one described above.

The proportion of participants with a \geq 2-step or \geq 3-step worsening of the DRSS score from Baseline will be analyzed using a similar method as described for the primary endpoint.

The AUC between Baseline and Week 24 in BCVA using the ETDRS will be analyzed by an analysis of covariance model with a main effect for treatment group, a classification factor for the DRSS category at Baseline (moderately severe or severe), and the Baseline BCVA value as a covariate.

Other exploratory endpoints will be summarized with descriptive statistics and/or counts and percentages of participants in each category of interest.

10.4.5. Planned Interim Analyses

No interim analysis is planned.

10.4.6. Multiple Comparison/Multiplicity

The analysis of the single primary endpoint to compare AKST4290 with placebo will be evaluated at the 2-sided 5% level of significance. Analysis of secondary endpoints will be adjusted for multiple endpoint or treatment group comparisons. Analysis of any exploratory endpoints will be exploratory in nature and not based on any formal hypothesis testing. Details of all analyses will be provided in the SAP.

10.5. Sample Size

Due to a dearth of studies with a 3-step improvement, as well as potential variabilities between each eye, the sample size is powered on the primary hypothesis comparing the difference between treatment arms (AKST4290 and placebo) in the proportion of participants with a ≥ 2 -step improvement of DR severity level on DRSS score in a single eye from Baseline as compared with Week 24. All calculations were based on the following fixed assumptions:

- Target 80% power.
- 2-sided alpha = 0.046.
 - It should be noted that to account for DSMB interim data reviews, the alpha spending approach has been adopted using an alpha reduction of 0.001 for each review (assuming a total of 4 reviews). The required sample size does not change if only three DSMB meetings are necessary.
- Test of 2 independent proportions based on the normal approximation.
- Based calculation on PANORAMA ([NCT02718326](#), [EYLEA Full Prescribing Information](#)), RISE/RIDE ([Nguyen 2012](#), [Wykoff 2018](#)), and VIVID/VISTA ([Korobelnik 2014](#), [Brown 2015](#)) study data.

The total sample size using the assumptions stipulated is approximately 80 enrolled participants to allow for a total of 69 completed participants. The randomization schema is 2:1 (AKST4290:placebo). Group sample sizes of 46 in the AKST4290 group and 23 in the placebo group will achieve approximately 80% power to detect a difference in group proportions of 24%. The proportion in the AKST4290 group is assumed to be 6% under the null hypothesis and 30% under the alternate hypothesis. The proportion in the placebo group is assumed to be 6%.

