4.2. Study Endpoints

4.2.1. Primary Endpoint

- The proportion of participants with a \geq 3-step improvement from Baseline on the DRSS score as compared with Week 24.

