4.2.2. Secondary Endpoints

- The proportion of participants with a \geq 2-step improvement from Baseline on the DRSS score as compared with Week 24.
- The proportion of participants progressing to the following vision-threatening complications that require treatment: CI-DME, PDR, and/or ASNV as assessed by SD-OCT, FP, and FA, as appropriate. The central reading center must confirm progression to CI-DME and PDR before treatment is initiated; progression to ASNV, and subsequent treatment, does not require photo documentation.
- Time to the following vision-threatening event(s) that require treatment: CI-DME, PDR, and/or ASNV.
- Safety as assessed by incidence and intensity of AEs.
- Effect of AKST4290 on diabetic kidney disease as assessed by changes in clinical laboratory values over time (e.g., eGFR, urine albumin to creatinine ratio [UACR]).
- Change from Baseline over time in the WPAI-GH questionnaire ([Section 17.5](#)).

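### The sample size section labels a ≥2-step calculation as the primary hypothesis; the primary endpoint is a ≥3-step improvement, for which no rate or power is given

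*Protocol*

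**What the plan says.** Protocol 4.2.1 makes the primary endpoint the proportion of participants with at least a "3-step improvement from Baseline on the DRSS score as compared with Week 24". Protocol 10.2 builds the only formal hypothesis on that endpoint: "The null hypothesis to be tested is that there is no difference between AKST4290 (A) and placebo (P) in the proportion of participants" reaching three or more steps. Protocol 10.4.2 defines the primary estimand the same way, and SAP 3.4.1.1 repeats the endpoint. Protocol 4.2.2 lists at least a "2-step improvement from Baseline on the DRSS score as compared with Week 24" as secondary, as does SAP 3.4.1.2.

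Protocol 10.5 states that "the sample size is powered on the primary hypothesis comparing the difference between treatment arms (AKST4290 and placebo"), but the outcome it then names is a two-or-more "step improvement of DR severity level on DRSS score in a single eye from Baseline as compared with Week 24". The same sentence gives the reason: few studies report 3-step improvement, and eyes may vary. The assumed rates are 30% on AKST4290 and 6% on placebo, at two-sided alpha 0.046. The conclusion is that "Group sample sizes of 46 in the AKST4290 group and 23 in the placebo group will achieve approximately 80% power" for a 24-point difference. On enrolment: "The total sample size using the assumptions stipulated is approximately 80 enrolled participants to allow for a total of 69 completed participants". SAP 4.5 carries the same text.

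The planned primary analysis (Protocol 10.4.2) is a Cochran-Mantel-Haenszel (CMH) test stratified by baseline DRSS category, in the ITT population, with missing Week 24 data counted as non-response. On the population, Protocol 10.3 says: "The Intent-to-Treat (ITT) Population will include all participants allocated to a randomized treatment".

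**The concern.** By Protocol 10.2 the primary hypothesis concerns three or more steps. A calculation for two or more steps is therefore not a calculation for the primary hypothesis, whatever the reason for using it. As labelled, the 80% is credited to the primary test, yet nothing in either document shows that it applies there: no ≥3-step response rate, difference or power appears. At stake is one stated design property, namely how likely the trial was to detect the effect on its primary endpoint.

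**Working it through.** **1. Reproduce the plan's figure.** Inputs from Protocol 10.5: p₁ = 0.30, p₂ = 0.06, n₁ = 46, n₂ = 23, two-sided alpha 0.046 (z = 1.995), normal approximation. With unpooled variance:

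- SE = √(0.30×0.70/46 + 0.06×0.94/23) = √(0.004565 + 0.002452) = 0.0838
- Power = Φ(0.24/0.0838 − 1.995) = Φ(2.865 − 1.995) = Φ(0.870) = 80.8%
- Placebo n for 80% power = (1.995 + 0.842)² × (0.0564 + 0.21/2)/0.24² = 22.55, rounded up to 23, so 23 + 46 = 69

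The stated 80% and 69 both reproduce. They belong to the ≥2-step rates.

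**2. Look for the ≥3-step counterpart.** Neither document has one. The only constraint that follows from the documents is logical: a ≥3-step responder is also a ≥2-step responder, so on the same eye and scale the planning rates cannot exceed 6% and 30%. That does not bound the power, because a lower placebo rate raises it. On the plan's own formula, 20% v 1% gives SE = √(0.20×0.80/46 + 0.01×0.99/23) = 0.0625 and power Φ(0.19/0.0625 − 1.995) = 85%.

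**3. Illustrate with assumed rates on the planned analysis.** The ≥3-step rates here are assumptions, not figures from the documents.

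- Group sizes: 80 × 2/3 ≈ 53 and 27 (ITT).
- Alpha: 0.046 (Protocol 10.5) to 0.05 (Protocol 10.4.6).
- Test: one-stratum CMH chi-square without continuity correction. With x responders in the active group, m responders in total and N = n₁ + n₂, the statistic is (x − n₁m/N)² / [n₁n₂m(N−m)/(N²(N−1))]. Power is the exact sum of binomial probabilities over all tables that reject.
- Dilution: if the assumed rates hold in completers, counting missing data as non-response multiplies both by 69/80 = 0.8625. This assumes equal dropout in the two arms.

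| Assumed rates (active v placebo) | Rates hold in ITT, alpha 0.046 to 0.05 | Completer rates diluted, alpha 0.046 to 0.05 |
|---|---|---|
| 15% v 3% | 30.5% to 37.1% | 21.3% to 29.2% |
| 20% v 4% | 50.6% to 52.9% | 40.1% to 44.6% |
| 20% v 1% | 76.2% to 81.5% | 62.4% to 71.5% |
| 30% v 6% (the plan's ≥2-step rates) | 76.9% to 77.0% | 68.1% to 68.4% |

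Using two strata with equal rates moves the ITT results for 15% v 3% to 29.8–33.3% and for 20% v 4% to 48.2–51.6%.

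**4. Read the last row.** On the planned test even the ≥2-step rates fall short of 80%. Part of any gap between a ≥3-step figure and 80% therefore comes from method (CMH against unpooled normal approximation, ITT against completers) and not from the endpoint.

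**The case against.** The strongest reply is disclosure. The sentence that uses the wrong label also names the ≥2-step single-eye outcome and says why it was used, and the power sentence ties the 80% to a 24-point difference at stated rates. Someone who reads the whole paragraph can see what was powered. Sizing a Phase 2 trial on a better-documented neighbouring endpoint is a defensible choice. All of that stands, and it rules out any reading that the substitution was hidden. It does not make a secondary endpoint the primary hypothesis, nor does it supply the missing power.

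A second reply is that the matter is now moot. SAP 1 and 4.6 record termination with three participants randomised and reporting by listings. This also stands and limits the weight of the point, although SAP 4.5, in a plan revised after termination, still carries the label.

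Two stronger readings are tempting, and the documents support neither.

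- A reader might infer that the primary endpoint was underpowered. With no ≥3-step rate given, that cannot be shown. Rate pairs that keep the plan's 5:1 ratio give low power, but nothing supports that ratio for three steps, and 20% v 1% comes close to or above 80%.
- A reader might infer that ≥3-step power cannot be stated at all until the plan says which eye, or which two-eye score, defines a responder. Protocol 7.1.1.3.1 and 10.5 do leave that open. But power conditional on assumed participant-level rates needs no eye definition; only the choice of plausible rates does.

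**Conclusion.** The label is wrong by the protocol's own definitions, and the 80% is not shown to apply to the primary test. The figure itself is correct for the ≥2-step planning rates under the unpooled normal approximation. Power for the ≥3-step endpoint is unknown: the assumed pairs tabulated above span roughly 31% to 82% if the rates hold in ITT, and are lower if completer rates are diluted by missing data. Those values rest on assumed rates, about 53 and 27 randomised, one stratum, and alpha between 0.046 and 0.05. They show how much depends on the missing rates; they do not estimate a shortfall. Severity is minor, because no primary test is performed and no result changes.

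**What to change.** In Protocol 10.5 and SAP 4.5:

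- Stop describing the ≥2-step calculation as the primary hypothesis, and label the 80% as planning power for a ≥2-step single-eye improvement.
- State power for the ≥3-step endpoint over a balanced range of assumed rates, including low placebo rates, under the planned analysis: stratified CMH, ITT, missing as non-response.
- Name the responder definition (which eye or score) that each set of rates refers to. The choice of definition and of sizing endpoint stays with the sponsor.

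If the SAP is already final, record the corrected label in the clinical study report. The cost is a change of wording and one short table. The stated power for the primary endpoint would rest openly on assumptions and may look less favourable than 80%. No additional participants or procedures are needed.
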